13.3 Sample Size and Power

98 individuals will be randomized. Accounting for up to 20% drop-out, power calculations are based on 78 participants.

Table 1. Minimum detectable absolute difference in mean change from baseline to 24 weeks between two groups (n=39 for Control group and n=39 for Exercise group) for the study endpoints, given an intra-individual correlation (ρ) of 0.5, 0.65 or 0.8, at 80% power, and adjusting for the number of hypotheses tests with 7 primary endpoints (type I error of 0.05/7).

Endpoint	Mean	SD	Minimum detectable absolute difference (% change)		
			$\rho = 0.5$	$\rho = 0.65$	$\rho = 0.8$
Distress (Perceived Stress Scale) ^a	19.23	6.77	5.41 (28.16%)	4.53 (23.56%)	3.42 (17.81%)
Distress (Hospital Anxiety and Depression Scale-anxiety subscale) ^b	7.4	3.9	3.12 (42.15%)	2.61 (35.27%)	1.97 (26.66%)
Distress (Hospital Anxiety and Depression Scale-depression subscale) ^b	5.8	3.5	2.87 (48.26%)	2.346 (40.4%)	1.77 (30.52%)
Quality of Life (36-item Short Form Survey- Physical Component Score) ^c	45.6	9.2	7.36 (16.14%)	6.16 (13.5%)	4.65 (10.21%)
IL-6 (pg/mL) ^d	2	0.7	0.56 (27.99%)	0.47(23.42%)	0.35 (17.70%)
VEGF (pg/mL) ^e	192	158.2	126.5 (65.88%)	105.8 (55.12%)	80(41.67%)
Salivary cortisol (nmol/L) ^d	4	0.6	0.48 (12.0%)	0.4 (10.04%)	0.3 (7.59%)

Mean and SD obtained from: ^a Perceived Stress Scale score in ovarian cancer survivors at the end of primary chemotherapy (111), ^b Hospital Anxiety and Depression Scale anxiety and depression subscale scores in ovarian cancer survivors towards end of primary chemotherapy (112), ^c 36-item Short Form Survey- Physical Component Score in our randomized controlled trial of exercise in ovarian cancer survivors (17), ^d biomarker levels in ovarian cancer survivors 6 months after primary treatment(113), and ^e VEGF levels in ovarian cancer survivors after completion of primary chemotherapy (114).

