We (PI: [name]) recently completed a randomized controlled trial of 144 physically inactive ovarian cancer survivors, randomized to six months of home-based, moderate-intensity exercise vs. control (17). At baseline, participants were on average 1.7 years post-diagnosis and exercised 31 minutes per week; 55% had advanced stage (III-IV). Intervention arm participants exercised a mean of 166 minutes per week of moderate exercise; 65% reported adhering to the goal of \geq 150 minutes per week, and 84% reported \geq 120 minutes per week (80% of goal). 83% of participants with stage III-IV ovarian cancer exercised at least 80% of goal, compared to 75% of participants with stage I-II ($p=0.41$), demonstrating that individuals with advanced-stage ovarian cancer can also exercise. Ovarian cancer survivors are highly motivated to adhere

Protocol 10045

to an exercise program and can exercise at recommended levels. Individuals in the exercise arm improved physical health-related quality of life, compared to a decreased physical health-related quality of life in control arm (mean 36-item Short Form Health Survey- Physical Component Score change of 1.8 ± 1.1 vs. -2.0 ± 1.2 , $P = 0.02$). A weakness of this study is that it relied on self-report for exercise adherence. We include actigraphy as an objective measure in our proposed study.

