The parameter β_1 is of our main interest and represents the mean difference in the outcome change from baseline to follow-up between participants in the exercise group and participants in the control group, adjusting for covariates Z such as age and BMI. We will first assess β_1 without any adjustments for Z (unadjusted analysis), and then add Z (adjusted analysis). Under the null hypothesis of no difference between intervention and control on the changes in the outcome measure, β_1 is equal to zero. If the exercise intervention indeed results in a greater reduction/increase in the outcome measure of interest in the exercise group compared with the control group, then β_1 is different from zero. Our statistical inference on β_1 will use the standard large-sample approximation, namely, two-sided Z-test and Z-confidence intervals based on the limiting Gaussian distribution.

Our analysis will be based primarily on intention-to-treat principle, but with minor modifications for practical considerations. The principles of ITT analyses are (i) keep participants in the intervention groups to which they were randomized, regardless of the intervention they actually received; (ii) measure outcome data on all participants; and (iii) include all randomized participants in the analysis (107). However, if data of individuals are lost, or are unavailable for other reasons immediately after randomization, then we will not include these individuals in the analysis (modified intention-to-treat). Under the modified intention-to-treat principle, enrolled participants who were later found to be ineligible will not be included in the primary analysis. To take adherence into account, we will also perform per-protocol analysis which includes only individuals who are considered adherent to the intervention assignment. Per-protocol analysis will not be our primary analysis, and we will report in detail the criteria for exclusion of individuals.

If we encounter missing data due to drop out or assay issues, we will apply mixed model regression using the available data in the analysis. In general, our analysis based on available data will be similar to the analysis using the individuals who do not have missing data (complete-case analysis) if the missing data mechanism is completely at random (108). When the

Protocol 10045

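### In Table 1 the HADS-depression detectable difference at ρ = 0.5 should read 2.80, not 2.87, and the prior trial's 3.8-point physical component difference lies below every value tabulated for that endpoint

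*Combined protocol and SAP*

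**What the plan says.** Section 13.3 bases power on 78 participants, 39 per arm, after allowing for up to 20% drop-out from 98. Table 1 gives the smallest difference in mean change detectable for each of seven primary endpoints, "given an intra-individual correlation (ρ) of 0.5, 0.65 or 0.8, at 80% power". The overall 0.05 is split equally among the seven, 0.05/7 each. Section 13.2 specifies a "two-sided Z-test and Z-confidence intervals based on the limiting Gaussian distribution". The parameter tested there "represents the mean difference in the outcome change from baseline to follow-up" between the arms.

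Two rows matter here.

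- **HADS-depression:** mean 5.8, SD 3.5. At ρ = 0.5 the entry is 2.87, with 48.26% beside it.
- **SF-36 physical component:** mean 45.6, SD 9.2. The entries are 7.36, 6.16 and 4.65. The footnote takes the mean and SD from "Physical Component Score in our randomized controlled trial of exercise in ovarian cancer survivors (17").

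The footnotes give sources for the means and SDs but none for ρ, and no column is named as the expected one.

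Section 2.3 describes the prior trial as a "randomized controlled trial of 144 physically inactive ovarian cancer survivors". It reports a "Physical Component Score change of 1.8 ± 1.1 vs. -2.0 ± 1.2" for exercise and control, with P = 0.02, and does not say what the ± values are. It adds: "At baseline, participants were on average 1.7 years post-diagnosis".

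**The concern.** The HADS-depression cell disagrees with itself: the absolute difference and the percentage beside it cannot both be right for a mean of 5.8. A stated detectable difference for a primary endpoint should be correct, even when the slip is small.

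The physical component row raises a question of interpretation. The only physical component effect that the protocol cites is the prior trial's difference of 1.8 − (−2.0) = 3.8 points. The smallest entry in the row is 4.65. By the table's own figures, then, the trial has less than 80% power for the effect that the team has already observed, and nothing in Section 13.3 says how much less. Without that figure, a reader of a non-significant result could take it as evidence against an effect of that size.

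**Working it through.** **Inputs.** From Table 1: 39 per arm, 80% power, type I error 0.05/7 = 0.00714, and the means, SDs and ρ values. From Section 13.2: a two-sided Z-test. From Section 2.3: changes of 1.8 ± 1.1 and −2.0 ± 1.2, P = 0.02, 144 randomized.

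**1. Reproduce the table.** The SD of change is SD × √(2(1−ρ)). The detectable difference is

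(z for 1−α/2 + z for 0.80) × SD × √(2(1−ρ)) × √(2/39).

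The two z values are 2.690 and 0.842, which sum to 3.532, and 3.532 × √(2/39) = 0.7998. For the physical component this gives 7.358, 6.156 and 4.654, against 7.36, 6.16 and 4.65 printed. The other cells agree to rounding or differ trivially (for example, HADS-depression at ρ = 0.65 is 2.342 against 2.346 printed, and VEGF at ρ = 0.65 is 105.86 against 105.8). HADS-depression at ρ = 0.5 is the one exception.

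**2. The HADS-depression cell.** At ρ = 0.5 the SD of change equals the SD.

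- Formula: 0.7998 × 3.5 = 2.799.
- The cell's own percentage: 48.26% × 5.8 = 2.799.
- The printed absolute value: 2.87 / 5.8 = 49.48%.

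The percentage is therefore right and the absolute value is wrong, by 2.87 / 2.799 − 1 = 2.5%. With 39 per arm, power is 80.0% at 2.80 and 82.4% at 2.87. A noncentral-t calculation does give 2.87 for this cell, but it does not explain the entry: it contradicts the printed 48.26%, and it would make HADS-anxiety at ρ = 0.5 equal to 3.20, where 3.12 is printed.

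**3. Power for 3.8 points.** Power = Φ(3.8 / (SD of change × √(2/39)) − 2.690), with SD 9.2 from Table 1:

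| ρ | SD of change | Standard error of difference | 3.8 / SE | Power |
|---|---|---|---|---|
| 0.5 | 9.20 | 2.083 | 1.824 | 0.193 |
| 0.65 | 7.70 | 1.743 | 2.180 | 0.305 |
| 0.8 | 5.82 | 1.318 | 2.884 | 0.577 |

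That is about 19%, 31% and 58%. These figures use only the table's own inputs and the 3.8 points in Section 2.3.

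**4. What the prior trial suggests about the columns.** The ± values fit only as standard errors: √(1.1² + 1.2²) = 1.628, 3.8 / 1.628 = 2.33, two-sided P = 0.020, as reported. Read as SDs with 72 per arm, z would be about 20.

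The number analysed is not given. I assume equal arms and 58 to 72 analysed per arm (about 20% loss to none). The SD of change is then √(n × (1.1² + 1.2²)/2):

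- n = 72: √(72 × 1.325) = 9.77, detectable difference 0.7998 × 9.77 = 7.81.
- n = 65: √(65 × 1.325) = 9.28, detectable difference 7.42.
- n = 58: √(58 × 1.325) = 8.77, detectable difference 7.01.

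Rounding of the standard errors (1.05 to 1.15 and 1.15 to 1.25) widens the range to about 6.7 to 8.2. The ρ = 0.5 column (SD of change 9.20, detectable difference 7.36) lies inside it. The ρ = 0.8 column needs an SD of change of 5.82, well below it.

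**The case against.** The strongest reply is that Table 1 is conditional. It shows what could be detected if ρ were 0.5, 0.65 or 0.8 and never calls 0.8 expected. Section 13.3 does not derive the 98 from any chosen ρ. Showing a range when ρ is uncertain is ordinary practice, and the column best supported by the prior trial is already printed first. All of this stands. No number in the physical component row is wrong.

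A reader might go further and infer that the prior trial fixes ρ at about 0.4 to 0.6, so that the 0.65 and 0.8 entries should be struck out. The documents do not support that. Section 2.3 does not give the arm split, the number analysed, the follow-up SD, or whether the reported changes are adjusted. With SD 9.2 at both times, 58 to 72 per arm gives ρ of about 0.44 to 0.55. But ρ = (s₀² + s₁² − SD of change²) / (2 s₀ s₁) moves with the follow-up SD: at an assumed 11, with 20% loss and the lower rounding limits, it is (84.64 + 121 − 69.84) / 202.4 = 0.67. The population differs as well: the prior trial averaged 1.7 years from diagnosis, while this trial enrols one to six months after primary treatment.

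It can also be said that no passage claims a null result would exclude 3.8 points, and that Section 2.1 presents the study as groundwork for a larger trial. That is true, and it lowers the stakes. It does not remove the gap, because the power for the team's own observed difference is stated nowhere and needs no back-calculated ρ.

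**Conclusion.** Two things hold, both minor.

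First, the HADS-depression entry at ρ = 0.5 is a misprint for 2.80. This is certain from the cell's own percentage and from the formula that reproduces the rest of the table. Nothing else depends on it.

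Second, the 3.8-point physical component difference lies below all three tabulated values, with power of about 19%, 31% and 58% across the ρ columns. This rests on 39 per arm, two-sided type I error 0.05/7 and an SD of 9.2, all taken from the plan.

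That 4.65 looks optimistic, and that about 7.0 to 7.8 is the better-supported detectable difference, is only indicative. It assumes that the ± values are standard errors, that the arms were equal with 58 to 72 analysed in each, and that the earlier population is a fair guide to this one. It does not show that the row was miscalculated, that ρ = 0.8 is ruled out, or that the trial should be larger.

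**What to change.** In Table 1, change the HADS-depression entry at ρ = 0.5 from 2.87 to 2.80 and leave its percentage as it is. Keep all three ρ columns for every endpoint. Below the table, add one sentence:

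*With 39 per arm and two-sided type I error 0.05/7, power for the 3.8-point difference seen in the prior trial is about 19%, 31% and 58% at ρ = 0.5, 0.65 and 0.8, so a non-significant physical component result cannot by itself exclude an effect of that size.*

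Optionally, compute ρ for the physical component directly from the prior trial's data and state which column it supports.

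The cost is one corrected cell and one sentence, with no change to enrolment, endpoints or analysis. The downside is a less favourable stated power for one primary endpoint.

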3.3.1 Primary Endpoints

1. Distress – mean change from baseline to 24 weeks between the exercise intervention and control group in the Perceived Stress Scale, and in the Hospital Anxiety and Depression Scale anxiety and depression subscales.
2. Quality of Life – mean change from baseline to 24 weeks between the exercise intervention and control groups in the 36-item Short Form Health Survey - Physical Component Score.
3. Biomarkers of angiogenesis- mean change from baseline to 24 weeks between the exercise intervention and control group in mean levels of IL-6, VEGF.
4. Nocturnal cortisol (biomarker of chronic stress) – mean change from baseline to 24 weeks between the exercise intervention and control group in mean evening cortisol level.

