13.2 Primary/Secondary Endpoints/Hypotheses and Analytical Methods

Descriptive statistics will be performed for baseline data, and distributions of outcome measures will be characterized using scatterplots, histograms, and summary statistics (e.g., mean, median, standard deviation, quartiles, range) to identify extreme outliers. Outcome variables will be log-transformed if their distributions are not symmetric. We will also examine if these measurements are balanced between the study intervention groups. The primary assessment of the exercise intervention effects will compare the average change from baseline to 24-week follow-up outcome measures (such as SF-36 physical component score) between the exercise group and the control group. Analyses will be intention-to-treat. The generalized estimating equations (GEE) modification of linear regression will be used in order to model the relationship between the outcome measures and exercise intervention and to account for the correlation within individual data over time. The GEE model will adjust for the measurement time and other potential covariates. Prior to fitting the GEE model, logarithmic transformation will be applied (if appropriate) to the outcome data to achieve approximate normality and variance stabilization. Our statistical inference on each outcome will use the standard large-sample approximation, namely, two-sided Z-test and Z-confidence intervals based on the limiting Gaussian distribution. More specifically, for the primary comparison between exercise group *vs.* control group, let Y_{ij} be the outcome measure (or log-transformed if appropriate) of interest for participant i at time j , where j is 0 for baseline and 1 for 24 week follow-up, X_i be the indicator variable for the intervention status (1=intervention, 0=control) and Z_i represent a vector of other potential adjusting variables (such as age, BMI). The linear model is as follows:

$$E[Y_{ij}] = \alpha_0 + \alpha_1 j + \beta_0 X_i + \beta_1 X_i j + \gamma^T Z_i, \text{Var}[Y_{ij}] = \sigma^2 \text{ and } \text{Cov}[Y_{ij}, Y_{kl}] = \rho \text{ if } i = k \text{ and } j \neq l, \text{ and } 0 \text{ otherwise.}$$

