13.4 Randomization

After baseline assessments are complete, participants will be randomized with equal probability to the exercise intervention (N=49) or wait-list control (N=49). Randomization will be blocked on stage (stages II-IIIA vs. IIIB-IV) and body mass index (<30 kg/m² vs. \geq 30 kg/m²) and will use permuted blocks with random size.

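### Section 13.2 sets no significance level or decision rule for the seven primary endpoints; the only level, 0.05/7, is a power input in Table 1, and Holm's step-down would keep the 0.05 bound with equal or better power

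*Combined protocol and SAP*

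**What the plan says.** Section 3.3.1 lists the primary endpoints without a hierarchy. Distress is measured "in the Perceived Stress Scale, and in the Hospital Anxiety and Depression Scale anxiety and depression subscales" (three endpoints). The others are the SF-36 physical component score (PCS), IL-6, VEGF and evening cortisol, which makes seven.

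Section 13.3 computes the detectable differences in Table 1 at 80% power, "adjusting for the number of hypotheses tests with 7 primary endpoints (type I error of 0.05/7"), with "n=39 for Control group and n=39 for Exercise group". This is the only place where a significance level appears.

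Section 13.2 defines the analysis: "Our statistical inference on each outcome will use the standard large-sample approximation, namely, two-sided Z-test and Z-confidence intervals". It gives no significance level, no confidence level, no correction and no rule for reading the seven results together. It also plans two analyses of the same parameter: "We will first assess β_1 without any adjustments for Z (unadjusted analysis), and then add Z (adjusted analysis"). It does not say which of the two is the primary test. Sections 13.5 to 13.7 add no multiplicity rule.

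**The concern.** A level used to size a trial binds the analysis only if the analysis section adopts it. Section 13.2 does not, so an analyst could test each endpoint at a conventional 0.05 and still comply with it. With seven co-equal primary endpoints, that would undo the error control that Table 1 assumes.

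If 0.05/7 is carried over as a fixed level for every test, the error is controlled but some power is given up. Holm's procedure tests the smallest p-value at 0.05/7, the next at 0.05/6, and so on, stopping at the first failure. It has the same 0.05 bound and gains most when several endpoints respond together. The synopsis hypothesises that pattern, with less distress, better quality of life and lower biomarker levels in the exercise arm. Power matters here because the detectable differences in Table 1 are large, at about 0.51 to 0.80 of the outcome SD.

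**Working it through.** **Inputs.** From section 13.3: 39 per arm, 80% power, level 0.05/7, within-person correlation ρ of 0.5, 0.65 or 0.8, and the SDs in Table 1. From section 13.2: two-sided Z-tests. From section 2.3: the earlier exercise trial's PCS changes of 1.8 and −2.0. The documents give no correlation between endpoints, so it is assumed and varied below.

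**1. Reproducing Table 1.** Detectable difference = (z(1 − 0.05/14) + z(0.80)) × SD × √(2(1 − ρ)) × √(2/39), with 2.690 + 0.842 = 3.532.
- Perceived Stress Scale (SD 6.77): 5.41, 4.53, 3.42, as printed.
- PCS (SD 9.2): 7.36, 6.16, 4.65, as printed.
- The other cells agree to rounding or very nearly, except the HADS depression subscale at ρ = 0.5. There 2.87 is printed and 2.80 computed. The printed 48.26% of 5.8 is also 2.80, so this looks like a slip and does not affect the point.
- A two-sided 0.05 would give 4.30 for the first stress-scale cell, and a one-sided 0.05/7 would give 5.05. Table 1 therefore used a two-sided 0.05/7.

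**2. Family-wise error, all seven nulls true.**
- Each test at 0.05, independent: 1 − 0.95⁷ = 30.2%. By simulation (400,000 trials, equal correlation between statistics): 27% at 0.3, 23% at 0.5, 15% at 0.8.
- Each test at 0.05/7, independent: 1 − (1 − 0.05/7)⁷ = 4.9%. Holm gives the same, because its first step is the same.

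**3. Holm thresholds.** 0.00714, 0.00833, 0.0100, 0.0125, 0.0167, 0.025, 0.05.

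**4. Mean power per truly affected endpoint, each effect at its Table 1 value** (expected Z of 3.532, simulated). The grouped structure assumes correlations of 0.6 among the distress scales, 0.4 between distress and PCS, and 0.1 elsewhere.

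| Real effects | Fixed 0.05/7 | Holm, independent | Holm, 0.3 | Holm, grouped | Holm, 0.8 |
|---|---|---|---|---|---|
| 1 | 80% | 80% | 80% | 80% | 80% |
| 3 | 80% | 83% | 82% | 82% | 82% |
| 4 | 80% | 84% | 84% | 83% | 83% |
| 7 | 80% | 92% | 90% | 90% | 87% |

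The chance of finding all four questionnaire effects rises from 41% to 52% (independent) or from 56% to 64% (grouped). The chance of at least one true rejection does not change: with four real effects and correlation 0.3 it is 98.6% either way.

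**5. A smaller effect.** The earlier trial's PCS difference is 1.8 − (−2.0) = 3.8, below every PCS cell in Table 1. Expected Z = 3.8 / (9.2 × √(2(1 − ρ)) × √(2/39)) = 1.82, 2.18 and 2.88 at ρ = 0.5, 0.65 and 0.8. Applying that standardised size to all four questionnaire endpoints is an assumption. Mean power then moves as follows:
- ρ = 0.5: 19% to 20–21%
- ρ = 0.65: 31% to 33%
- ρ = 0.8: 58% to 62%

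With the grouped correlations the gain is about 2 to 4 points. With independent statistics it is about 1 to 4.

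**6. Test and interval disagreement.** A 99.29% interval corresponds to 1 − 0.05/7. With effects at their Table 1 values, at least one endpoint is significant by Holm while its 99.29% interval includes zero in about 14–17% of trials with four real effects and 50–58% with seven (independent or grouped correlations).

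**The case against.** Three objections are fair.

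- **A fixed 0.05/7 is not an error.** It controls the family-wise error under any dependence and keeps each test consistent with its interval. That is a legitimate reason to prefer it, and Holm is a refinement. This stands.
- **The largest gain needs all seven effects to be real and as large as Table 1 assumes.** For VEGF that means a change of 42% to 66% of the mean. With one real effect there is no gain, and with four effects of the earlier trial's PCS size it is only a few points. This stands and limits the size of the claim.
- **Holm uses more of the error allowance.** With four of seven effects real and correlation 0.3, the actual family-wise error is 4.0% under Holm and 2.1% under fixed 0.05/7. Both are within the 0.05 bound, so this is no reason against Holm.

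A reader might infer that the plan has committed to plain Bonferroni and so turned step-down testing down. The documents do not show this: the caption describes a power calculation, and 0.05/7 is equally Holm's first-step level. A reader might also call the change free. It costs no patients and no error control, but section 13.2 promises confidence intervals and Holm has no simple matching simultaneous ones.

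**Conclusion.** The concern holds in two parts of unequal weight.

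The firmer part is the omission. Section 13.2 has no level and no decision rule, and it leaves open whether seven or fourteen p-values count, since each endpoint has an unadjusted and an adjusted test. The 15% to 30% family-wise error is what conventional 0.05 testing would produce over assumed correlations from 0.8 down to 0. It does not follow that the sponsor intends this, because the Table 1 caption points the other way.

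The second part is a worthwhile improvement. That Holm keeps the 0.05 bound and rejects everything a fixed 0.05/7 rejects is a mathematical property and needs no assumption about correlation. The size of the power gain does rest on assumptions: how many effects are real, how large they are, and how the endpoints correlate. It runs from nothing with one real effect to about 12 points per endpoint with seven independent ones.

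The planned enrolment and Table 1 are not put in doubt.

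**What to change.** Add to section 13.2 text to this effect:

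> The seven primary endpoints are tested with Holm's step-down procedure at a two-sided family-wise level of 0.05. The smallest p-value is compared with 0.05/7, the next with 0.05/6, and so on, stopping at the first failure. One β₁ analysis per endpoint [unadjusted or adjusted, to be named here] enters the procedure; the other is supportive. Nominal 95% and 99.29% confidence intervals are reported for each endpoint. Where a 99.29% interval and the Holm test disagree, the Holm test governs.

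In section 13.3, keep Table 1 and describe its figures as conservative first-step values.

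The cost is a few sentences, with no added participants or data. The small downside is the possible disagreement between test and interval, which the last sentence settles. If the sponsor prefers test and interval always to agree, a fixed 0.05/7 written into section 13.2, with the same choice of β₁ analysis, would also close the gap in error control at the price of the power shown above.
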